## 4.5 Discontinuation of Subjects and Stopping Criteria

A subject will be withdrawn from the study if more than 12 days elapse between the onset of weakness and planned imlifidase administration.

The subjects have the right to withdraw from the study at any time for any reason without the need to justify their decision. However, the investigator should record the reason for the subject's withdrawal, if possible. The investigator also has the right to withdraw subjects. In either event, the investigator must notify Monitor.

Minor infusion-related reactions have been observed in some patients receiving imlifidase for other indications. These are usually mild and include chest discomfort, flushing, pharyngeal oedema and dyspnea. More severe reactions can occur.

If a minor infusion-related reaction (Common Terminology Criteria for Adverse Events (CTCAE) grade 1 or 2) is suspected the infusion should be temporarily stopped and the patient should be observed for clinical signs of allergic reactions. If a significant infusion-related reaction or anaphylactic reaction occurs (CTCAE grade 3 or higher) then the imlifidase therapy should be discontinued immediately.

The patient should be treated by the investigator according to local practice for an allergic reaction or a severe allergic reaction/anaphylaxis, respectively. If the symptoms resolve, the infusion can be resumed. If the symptoms persist or worsen, then the drug infusion should not be restarted.

A subject that prematurely discontinues participation must, if possible, be called in for a last visit and undergo the assessments and procedures scheduled for visit 9 (180 days after treatment with imlifidase). Even if the subject is not able to attend, the End-of-Study Form in the electronic Case Report Form (eCRF) must be completed. Subjects who for a medical reason cannot comply with the protocol procedures will be followed by best procedure to retrieve safety and efficacy data.

Subjects withdrawn from the study before visit 6 (29 days after treatment with imlifidase) may be replaced, not using the same subject number, in order to reach approximately 30 evaluable subjects.

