#### **12.3.4.4 Time to improvement by at least one, two and three grade(s) on the GBS DS**

Time to improvement by at least one, two and three grade(s), respectively, on the GBS DS will be presented using Kaplan-Meier curves.

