## 1 Introduction

Guillain-Barré Syndrome (GBS) is an acute, paralyzing, inflammatory disease of the peripheral nervous system usually preceded by an infection or other immune stimulation that induces an aberrant autoimmune response targeting peripheral nerves and their spinal roots. GBS is a rapidly progressive disorder often leading to a severe paralysis of the arms and legs. Most GBS patients have sensory disturbance (tingling or numbness or ataxia) and pain, and some patients have double vision or problems with swallowing. GBS may also paralyse the respiratory muscles, leading to intensive care unit admission and mechanical ventilation.

After onset, GBS patients have a mortality rate of 3-5%. Two thirds of the patients have severe symptoms resulting in their inability to walk unaided, and 20-30% require mechanical ventilation for a period ranging from weeks to months. Progression of weakness in GBS is usually rapid and reaches a nadir within 4 weeks in patients, but the majority develop their maximum deficit within 2 weeks.

To treat GBS, both general medical care and immunological treatment are recommended. Intravenous Immunoglobulin (IVIg) and Plasma Exchange (PE) are the two main treatments. Imlifidase is an immunoglobulin G-degrading enzyme derived from *Streptococcus pyogenes* that with strict specificity cleaves all four human subclasses of IgG. Imlifidase cleaves human IgG below the hinge region thereby generating one F(ab')2 fragment and one Fc-fragment which does not bind to Fc-receptors and does not activate complement.

This study is designed to evaluate the safety, tolerability, and efficacy of intravenous dosing of imlifidase in GBS subjects. Additionally, pharmacokinetics (PK) and pharmacodynamics (PD) will be assessed.

In addition, a comparison to an externally matched cohort of GBS subjects treated with IVIg (IGOS database) will, if feasible, be conducted to evaluate the efficacy of imlifidase plus IVIg in combination. If such an indirect comparison study is feasible, details pertaining to the comparison will be outlined in a separate non-interventional study protocol.

This document presents the planned statistical analyses for Hansa Biopharma AB, study 15-HMedIdeS-09: An open-label, single arm, multi-centre, phase II study investigating safety, tolerability, efficacy, pharmacodynamics and pharmacokinetics of imlifidase (IdeS) in patients with Guillain-Barré Syndrome (GBS), in comparison with matched control patients.

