## 2.4 Data pre-processing

Difference between the value at each assessment and value at baseline for the efficacy parameters as an absolute change and percentage change will be calculated as:

$$\text{Absolute change at visit } x = \text{Value at visit } x - \text{value at baseline}.$$

$$\text{Change in \% at visit } x = \frac{\text{absolute change at visit } x}{\text{value at baseline}} \cdot 100.$$

The proportion of subjects with improvement since baseline at each visit will be calculated as:

$$\text{Proportion at visit } x = \frac{\text{number of subjects with improvement at visit } x}{\text{number of subjects at baseline}}.$$

Mean difference from baseline to each visit will be calculated as:

$$\text{Mean difference at visit } x = \frac{\text{sum of absolute change from baseline at visit } x}{\text{number of subjects at visit } x}.$$

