## 4.7 Efficacy analysis

### 4.7.1 GBS Disability Score (GBS DS)

The GBS Disability Score (GBS DS) used for the efficacy endpoints will be assessed for all subjects as per the schedule of assessments. The score is defined as follows:

0 = Healthy

1 = Minor symptoms and capable of running (subjects must be asked to run)

2 = Able to walk independently 10 meters or more but unable to run

3 = Able to walk more than 10 meters across an open space with help

4 = Bedridden or chair bound

5 = Needing mechanical ventilation

6 = Dead

Summary statistics will be presented in tables for the actual values and absolute change from baseline by time point. Also, shift tables will be presented to show the change from baseline as compared to post-baseline visits for the GBS DS.

In addition, the number and percentages of subjects with improvement of at least one, two or three grades, respectively, on the GBS DS will be presented by time point.

Similarly, the number and percentage of subjects able to walk unaided (GBS DS  $\leq 2$ ) and run (GBS DS  $\leq 1$ ), respectively, will be presented by time point.

Lastly, the following Kaplan-Meier analysis summary tables and plots will be presented:

- Time to improvement by at least one grade on the GBS DS
- Time to improvement by at least two grades on the GBS DS
- Time to improvement by at least three grades on the GBS DS
- Time to walk independently (GBS DS  $\leq 2$ )
- Time to run (GBS DS  $\leq 1$ )

Study end/discontinuation will be considered as censoring for subjects that do not have the event. In addition, the survival function will start at 0, since all these are “positive” events.

For each endpoint two separate Kaplan-Meier plots will be presented, one up to Day 29 (collected part of Visit 6) and one up to Day 360 (collected as part of Visit 10), including the subjects at risk at specific timepoints. Also censored observations will be marked as such on the plot.

The summary tables for the corresponding Kaplan-Meier analysis will include the following for specific timepoints up to Day 360: subjects at risk, number of subjects with events, censored observations, proportion estimates and associated pointwise 95% confidence interval (CI).

A separate table will present the number of subjects included in the analysis with corresponding number of events, number of censored observations and summary statistics for the time to event (minimum, maximum, median and associated 95% CI, quartiles).

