## 5 Interim analyses

No interim analyses are planned.

The main analyses for the CSR will be based on all data up to and including visit 9 (Day 180). To note, at time of the main analysis some subjects will have also the visit 10 (Day 360) performed, ie will have completed the study. All data available at time of database lock will be included in the main analyses, meaning that some subjects will have completed the study.

Remaining data from visit 10 (Day 360) will be included in an addendum to the CSR.

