## 6 Deviations from protocol analysis

The following changes have been considered in current SAP as compared to study protocol:

- Minor wording on the FAS definition as compared to protocol. Change has been made in order to make the definition clearer.
- Percentage change from baseline summaries will be not presented for the vital signs and laboratory assessment results (ie clinical chemistry, haematology and urinalysis).
- The main analyses for the CSR will be based on all data included in the database at time of database lock, including visit 10 (Day 360) data for subjects that reached that stage (ie completed the study).

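### The five Kaplan-Meier recovery endpoints have no rule for death; if a death before recovery is censored in the ordinary way, the tabulated proportion recovering is biased slightly upward

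*SAP*

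**What the plan says.** SAP 4.7.1 plans Kaplan-Meier tables and plots for time to improvement by at least one, two and three grades on the GBS disability score (GBS DS), time to walk independently, and time to run. The curves start at zero and rise, so the reported quantity is one minus the Kaplan-Meier estimate (1-KM).

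The only censoring rule is "Study end/discontinuation will be considered as censoring for subjects that do not have the event". At each listed timepoint up to Day 360 the tables show "subjects at risk, number of subjects with events, censored observations, proportion estimates and associated pointwise 95% confidence interval (CI"). A subject is therefore either an event or a censored observation; there is no third category. The same section scores death as grade 6 of the GBS DS but does not say how a death enters these analyses.

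No other section fills the gap:

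- Protocol 12.3.4.4 says only that time to improvement "on the GBS DS will be presented using Kaplan-Meier curves", and 12.3.4.5 and 12.3.4.6 say the same for walking and running.
- Protocol 4.5, on discontinuation, reads as if the subject is alive ("A subject that prematurely discontinues participation must, if possible, be called in for a last visit") and does not classify death.
- The imputation rules in SAP 4.1.3 cover dates of adverse events and medications only.
- The list of departures from the protocol in SAP 6 is silent on the point.

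**The concern.** Death ends participation, so a programmer who follows SAP 4.7.1 would normally censor a subject who dies without the event at the date of death. Kaplan-Meier treats a censored subject as still able to have the event later, at the same rate as those who remain. A subject who has died cannot recover. The curve then estimates recovery in a population where nobody dies, and is read as the proportion of treated subjects who recover.

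The study tests no hypothesis, so these descriptive curves and tables are part of its efficacy result. They are the plan's estimate of how many subjects improve, walk or run again, and when. Any error from this source is in the favourable direction. Death is also foreseeable here. The SAP's own introduction says "After onset, GBS patients have a mortality rate of 3-5" per cent, so a rule should exist before it is needed.

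A death after the event does not affect that endpoint's curve. The number of relevant deaths therefore differs between the five endpoints.

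**Working it through.** The plan states no figure for these endpoints, so there is nothing to reproduce. The check compares 1-KM, with deaths censored at the date of death, against estimators that give the dead no chance of recovery.

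**Inputs from the documents.** N = 30 (SAP 2 and 2.2). Mortality 3-5% with no time horizon (SAP 1). About 20% unable to walk after 6 months (Protocol 1.1), so 24 of 30 is a reasonable level for walking.

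**Assumptions, not in the documents.** Either 6, 12, 18, 24 or 27 of 30 recover by Day 180. Recoveries at Days 8, 15, 29, 57, 92 and 180 are respectively 0,1,1,1,1,2; 1,2,2,3,2,2; 1,3,4,4,3,3; 2,4,5,6,4,3; and 3,5,6,6,4,3. One or two deaths occur before recovery, at Day 5, 40 or 120. There is no other loss before Day 180.

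**Formulas.** With d recoveries among n at risk at each event time, 1-KM = 1 - product of (1 - d/n). Aalen-Johansen = sum of S x d/n, where S is the probability of being alive and not recovered just before that time. With no other loss, Aalen-Johansen at Day 180 equals recoveries/30. Keeping the dead in the risk set as not recovered gives the same value.

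**Hand check: 24 recover, one death at Day 120.** By Day 92, 2+4+5+6+4 = 21 have recovered, leaving 9 of 30. The death leaves 8 at risk, of whom 3 recover at Day 180.

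- 1-KM: 1 - (9/30)(5/8) = 81.25%
- Aalen-Johansen: 21/30 + (8/30)(3/8) = 80.0%
- Dead kept at risk: 1 - (9/30)(6/9) = 80.0%

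**The two extremes.** Smallest: 6 recover, one death at Day 120, 1 - (26/30)(23/25) = 20.27% against 20.0%. Largest: 27 recover, two deaths at Day 5, 1 - 1/28 = 96.43% against 90.0%.

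**All scenarios at Day 180.** Ranges run over the three death times; the half-width is 1.96 x sqrt(p(1-p)/30).

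| Recover | True % | Excess, one death (points) | Excess, two deaths (points) | 95% half-width (points) |
|---|---|---|---|---|
| 6 | 20.0 | 0.3-0.7 | 0.6-1.4 | 14.3 |
| 12 | 40.0 | 0.35-1.4 | 0.7-2.9 | 17.5 |
| 18 | 60.0 | 0.7-2.1 | 1.5-4.3 | 17.5 |
| 24 | 80.0 | 1.3-2.8 | 2.9-5.7 | 14.3 |
| 27 | 90.0 | 2.0-3.1 | 5.0-6.4 | 10.7 |

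The largest excess is 3.10/10.7 = 29% of the half-width with one death and 6.43/10.7 = 60% with two.

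**How many such deaths to expect.** 30 x 0.03 = 0.9 and 30 x 0.05 = 1.5 deaths in all. Only deaths before the event count, and that share is not documented. Let f be the share and q = f x mortality. Then P(at least 1) = 1 - (1-q)^30, and P(at least 2) = 1 - (1-q)^30 - 30q(1-q)^29.

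| Share f | Expected deaths before event | P(at least 1) | P(at least 2) |
|---|---|---|---|
| One half | 0.45-0.75 | 37-53% | 7-17% |
| One quarter | 0.23-0.38 | 20-31% | 2-5% |

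**Average effect.** A simulation of 4,000 trials per setting assumed 50% or 80% recovery and death times uniform over Days 1-180. The mean excess was 0.5-0.8 points at 3% mortality and 0.8-1.3 points at 5%.

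**The case against.** The strongest reply is that this is an ambiguity, not a stated error. The SAP never says that a death is censored at its date. Since death is a grade on the scale, it could be treated as an observed state of non-recovery and carried to the end of follow-up, with no bias. That stands, and it is why the point is conditional. But the tables offer only events and censored observations, and nothing in the text directs the programmer away from censoring at the last date in the study.

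A second reply is that deaths stay visible elsewhere: grade 6 in the GBS DS summaries, the swimmer plot, the counts of adverse events leading to death, and the deaths listing. This is true. It lets a reader detect the problem but does not correct the tabulated proportions.

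Two stronger readings are tempting and should not be drawn:

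- A reader might expect disagreement with the by-visit improvement proportions to prove the bias, because SAP 2.4 divides by the "number of subjects at baseline" and so keeps the dead in the denominator. It would not prove it. Those proportions count subjects improved at a visit, whereas Kaplan-Meier counts first improvement. The two also differ when a subject worsens again (Protocol 1.1 cites 8-16% deteriorating after IVIg, even after initial improvement) and when a living subject drops out.
- A reader might infer that median recovery times would shift materially. That depends on the assumed recovery schedule and on how a curve at exactly 50% is handled, which the documents do not state. No claim about the median is made here.

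**Conclusion.** The concern holds in a limited form. SAP 4.7.1 leaves death without a rule, and the ordinary application of its censoring rule biases the five 1-KM proportions upward, never downward. The size is about 0.3 to 3.1 points with one death before the event and 0.6 to 6.4 with two, under assumed recovery of 6 to 27 of 30 and no other loss before Day 180. The top of that range needs 90% recovery and two deaths at Day 5. In every scenario the excess is smaller than the 95% half-width, and it is zero if nobody dies before the event.

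A reader might go further and infer that the SAP instructs censoring at death, or that the study's conclusions are unsafe. The documents support neither: the instruction is absent, and no test or sample-size target depends on these curves. What remains is a small error in the favourable direction that one sentence would prevent.

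**What to change.** Add to SAP 4.7.1: death before the event is not censored at the date of death. Then choose one of two methods.

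1. Keep such subjects in the risk set as not recovered to the end of the follow-up horizon (Day 360). This retains the protocol's Kaplan-Meier method.
2. Use the Aalen-Johansen cumulative incidence with death as a competing event. As the protocol names Kaplan-Meier, list this in SAP 6, under "The following changes have been considered in current SAP as compared to study protocol".

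The two agree when there is no other loss before the timepoint. If living subjects leave early, the second is cleaner, because under the first the retained deaths carry slightly too much weight. Leave the existing censoring in place for subjects who leave alive or have not yet reached visit 10. Under either method, count and mark deaths separately from other censored observations in the tables and plots.

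The change log in SAP 10 shows that version 2.0 was finalised during the main analysis. For outputs already run, report the corrected figures in the CSR as a labelled post hoc change beside the planned ones. Then apply the rule in the later report: "Remaining data from visit 10 (Day 360) will be included in an addendum to the CSR".

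The cost is a sentence, a small programming change and, for the second method, one entry in SAP 6. No new data are needed. Recovery figures become slightly less favourable if a subject dies before recovery; if none does, they do not change.

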##### 3.1.3 Assessment Procedures

The subjects will be followed clinically on Days 1-8, 15, 29, 57, 92 and 180 days after imlifidase infusion and additionally with a 360-day telephone contact to assess GBS DS, R-ODS, capture health status in a questionnaire and AEs.

After study completion, all study subjects will be followed up regularly according to clinical practice at the site in question.

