## **3.5 End-of-Study**

The planned end-of-study is defined as the last telephone contact has been completed (visit 10). Hansa Biopharma will ensure that an end-of-study notification is submitted to the concerned Regulatory Authority (RA) and Independent Ethics Committee (IEC)/ Institutional Review Board (IRB) according to local requirements.

For procedures in case of premature termination or suspension of the study, see [Section 13.4](#).

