### Visit 10 End-of-study, Day 360 (Telephone Contact) (+14 days)

A telephone contact for safety evaluation will be performed approximately 12 months (Day 360) after infusion of imlifidase.

The following activities and assessments will be performed:

- AE and Concomitant Medication
- GBS DS and R-ODS scale
- EurQol EQ-5D Health Questionnaire
- Confirm that the diagnosis is still GBS (yes/no), if no, specify which primary diagnosis the patient has been given

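### The Kaplan-Meier recovery endpoints are censored at study end or discontinuation, not at the last GBS DS score, so recovery can be understated when a subject's closing date falls after a missed visit

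*SAP*

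**What the plan says.** SAP 4.7.1 plans Kaplan-Meier tables and plots for improvement by at least one, two and three grades, for walking independently and for running. The only censoring rule is "Study end/discontinuation will be considered as censoring for subjects that do not have the event". Each endpoint gets two plots, "one up to Day 29 (collected part of Visit 6) and one up to Day 360 (collected as part of Visit 10"), and the tables report proportions, medians and 95% confidence intervals. The last GBS DS assessment is not mentioned. SAP 4.1.3 leaves missing data missing and sets no censoring date.

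The protocol fixes when GBS DS can be known:

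- Section 3.1.3: "The subjects will be followed clinically on Days 1-8, 15, 29, 57, 92 and 180 days after imlifidase infusion", plus the Day 360 telephone call.
- Section 3.5: "The planned end-of-study is defined as the last telephone contact has been completed (visit 10"). The Visit 10 list in Section 6.1 includes "GBS DS and R-ODS scale".
- Section 4.5: a subject who leaves early "must, if possible, be called in for a last visit and undergo the assessments and procedures scheduled for visit 9". Visit 9 includes GBS DS. The same paragraph adds: "Even if the subject is not able to attend, the End-of-Study Form in the electronic Case Report Form (eCRF) must be completed".

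SAP Section 5 runs the main analysis on all data available at database lock, when only some subjects will have reached Day 360.

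**The concern.** A subject can be counted as event-free only up to the last time someone scored GBS DS. After Day 8 the gaps between assessments run from 7 days (Day 8 to Day 15) to 180 days (Day 180 to Day 360). If a subject misses a visit, has no last assessment, and is given a discontinuation or study-end date after that visit, the stated rule keeps them in the denominator when others are found to have recovered. The estimated recovery hazard at that visit is then too small.

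All five recovery curves, their medians and their intervals are exposed. The by-visit improvement proportions do not compensate: SAP 2.4 divides by the number of subjects at baseline, so a missing subject already counts there as not improved. Replacing subjects withdrawn before Day 29 (Protocol 4.5) does not remove them either, because the FAS keeps every dosed subject with confirmed GBS.

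A subject still in follow-up at the main lock has neither a study end nor a discontinuation, so the rule gives no date at all.

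**Working it through.** The plan has no figure to reproduce: no sample-size calculation, dropout rate or assumed recovery curve. The check asks who is affected and then sizes the effect under stated assumptions.

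**1. Who has a gap between the last GBS DS and the censoring date?**

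| Subject without the event | Last GBS DS versus censoring date | Effect |
|---|---|---|
| Completes the Day 360 call | same contact | none |
| Discontinues and attends the last visit | same visit | none |
| Discontinues with no last visit, dated before the next scheduled visit | gap, but no event time falls inside it | none |
| Discontinues or is closed with no last visit, dated on or after a missed visit | gap contains an event time | recovery lowered |
| Ongoing at main lock | no date defined | undefined |

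**2. Formula.** At a visit with *n* assessed, unrecovered subjects, *e* of whom have recovered, the Kaplan-Meier factor should be 1 − e/n. If *L* unassessed subjects are carried along, it becomes 1 − e/(n + L).

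**3. Assumed curve.** N = 30, with cumulative walkers 3, 6, 11, 16, 20, 24 and 26 at Days 8, 15, 29, 57, 92, 180 and 360. The value 24/30 = 80% at Day 180 matches the protocol's background statement that 20% cannot walk after 6 months. The other values are assumptions. Subjects lost are assumed to recover at the same rate as those assessed. Censoring at the last assessment then gives 80.0% at Day 180 and 86.7% at Day 360.

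**4. Worked cases.**

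*Two subjects last scored at Day 180 and closed after Day 360.* Six are unrecovered at Day 180, four of them are assessed later, and e = 4 × 2/6 = 1.333.
- Last assessment: 1 − 0.20 × (1 − 1.333/4) = 86.7%.
- Closing date: 1 − 0.20 × (1 − 1.333/6) = 84.4%, a difference of −2.2 points.

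*Two subjects last scored at Day 29 and dated Day 60.* Nineteen are unrecovered, 17 are assessed at Day 57, and e = 17 × 5/19 = 4.474. Unrecovered at Day 180: 19/30 × (1 − 4.474/19) × 10/14 × 6/10 = 0.2075. Recovery is 79.2% against 80.0%.

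The same arithmetic for other dates:

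| Lost | Last scored | Recorded date | Day 180 difference | Day 360 difference |
|---|---|---|---|---|
| 2 | Day 29 | Day 40 | 0.0 | 0.0 |
| 2 | Day 29 | Day 60 | −0.8 | −0.5 |
| 2 | Day 29 | Day 95 | −1.9 | −1.3 |
| 2 | Day 29 | Day 180 | −4.6 | −3.0 |
| 2 | Day 180 | Day 200 | 0.0 | 0.0 |
| 2 | Day 180 | after Day 360 | 0.0 | −2.2 |
| 5 | Day 29 | after Day 360 | −11.4 | −13.2 |

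**5. Average over random loss.** 2000 simulated trials per row, with non-informative loss spread evenly from Day 8 to Day 360. Differences are in percentage points, Day 180 / Day 360.

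| Loss | Dated at actual loss | Dated 14 days after first missed visit | All dated at the end of the Day 360 window |
|---|---|---|---|
| 5% | 0.0 / 0.0 | −0.2 / −0.4 | −0.7 / −1.0 |
| 10% | 0.0 / 0.0 | −0.5 / −0.7 | −1.3 / −2.0 |
| 20% | 0.0 / 0.0 | −1.1 / −1.5 | −2.6 / −3.9 |

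**6. Deaths pull the other way.** If a death is censored as an ordinary discontinuation, Kaplan-Meier treats the subject as still able to recover. With *k* deaths after Day 15 among the 24 then unrecovered, Kaplan-Meier stays at 80.0% at Day 180. The cumulative incidence is 6/30 + (18/30) × (24 − k)/24, which is 77.5% for one death and 75.0% for two. The protocol's 3-5% mortality is about 1 to 2 of 30 subjects.

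**The case against.** The strongest reply is that the sentence names the reason for censoring and does not fix the date, so a programmer may already use the last assessment. The documents allow that reading. Protocol 4.5 requires the End-of-Study Form but says nothing about how it is dated, and the SAP refers to discontinuation, not to form completion. A reader might infer that the SAP decided against the last assessment, or that sites will date forms late. Neither is documented. What stands is that the written rule points to study end or discontinuation, no derivation is given, and the date is undefined for subjects ongoing at lock. The same edit cures either reading.

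A second reply is that the consequence is small. Nothing is tested, and the analysis is single-arm and descriptive. With 30 subjects a 95% interval is about ±14 points at 80% (1.96 × √(0.8 × 0.2/30)) and ±18 at 60%. Censored observations are marked on the plots and numbers at risk are shown. All of that is fair and limits the weight of the point. It does not remove it, because the Kaplan-Meier proportions, medians and intervals are themselves the reported results.

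**Conclusion.** The point holds as a conditional one: recovery *can* be understated. It needs a subject without the event, no last-visit GBS DS, a recorded date on or after a missed visit, and recoveries in others at that visit. Under an assumed 10% loss the average effect runs from 0 to about −2 points. At 20% loss with every form dated at the end of the Day 360 window it reaches about −4. The dropout rate, the dating practice and every point of the curve except 80% at Day 180 are assumptions.

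Two stronger readings are not supported. One is that recovery will be 5 to 6 points too low. For running by Day 360, a 5.0-point shortfall (75.0% against 80.0%) needs 18 of 30 running at Day 180, 3 of the other 12 lost and all closed after Day 360, and half of those reached newly running. For Day 29, 6.0 points needs 3 of 30 last seen on Day 8 and closed after Day 29, 60% recovery, and no recovery by Day 8. The other is that the net bias of the planned curves is downward: a single death censored in the ordinary way moves the Day 180 figure up by 2.5 points, so the net direction is not established.

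This is worth correcting because a definite and better rule is available at almost no cost. It does not undermine the study's conclusions.

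**What to change.** Replace the censoring sentence in SAP 4.7.1, for all five endpoints and for both the Day 29 and Day 360 plots, with:

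> Subjects without the event, including those ongoing at database lock, are censored at the date of their last non-missing GBS DS assessment.

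Add a separate sentence saying that deaths (GBS DS 6) are not treated as ordinary censoring. Either keep them in the risk set as non-events to the end of the horizon, or report cumulative incidence with death as a competing event. Without this second sentence, the edit would remove a possible downward bias and leave the upward one.

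The cost is two sentences in the SAP and one derivation in the time-to-event dataset. No new data are needed. Because SAP version 2.0 was finalised during the main analysis, the change should be recorded as a deviation in the CSR or applied in the Day 360 addendum. A count of subjects whose censoring date changes would show whether it mattered.
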